# **Aim and Objectives:**

Aim: This study aims to establish the efficacy of nitroglycerine skin patch as a NO donor in addition to dinoprostone for induction of labor.

Objectives: The primary outcome of the study is to compare the changes occurring to the cervix through the progression in the Bishop's score between NO donor (nitroglycerine patch) vs placebo; in combination with a well-established method of induction (Dinoprostone).

The secondary objective of the study is to observe and report possible fetal and maternal side effects that may be associated. This will establish the safety and tolerability of NO donors.

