#### **Management and Monitoring:**

If the case managed to initiate labor, reevaluation of the mother and the fetus will be carried out. And the mother will be monitored according to routine management via the partogram.

If there is a progression in the Bishop's with no onset of labor, induction will be initiated by amniotomy. Provided that the liquor is clear, oxytocin intravenous drip will be initiated. If the liquor is meconium stained, thorough fetal monitoring will take place. Persistent abnormal fetal CTG or deeply stained liquor will be referred to theater for cesarean section.

The fetus will be monitored by the cardiotocography. The mother will be evaluated by the vital signs and other signs of headache, palpitation, dizziness, GI upset ....etc.

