# Both groups will be compared regarding:

- Time from the start of labor induction to vaginal delivery
- > Time from start of drug administration to the earliest uterine contraction
- ➤ Progression of Bishop's score
- ➤ Duration of the first, second and third stages of labor
- ➤ Whether they eventually need to have a cesarean section or not.
- ➤ Incidence of maternal complications, namely; headache, nausea, postpartum hemorrhage,
- > Neonatal outcome through Apgar score at 1 and 5 minutes after delivery.

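### The maternal safety comparison names only headache, nausea and postpartum hemorrhage, so palpitation, dizziness and vital signs are monitored but not planned for comparison between arms

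*Protocol*

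**What the plan says.** Three sections of the protocol bear on this point.

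- **Aim and Objectives.** "The secondary objective of the study is to observe and report possible fetal and maternal side effects that may be associated". The next sentence states the conclusion to be drawn: "This will establish the safety and tolerability of NO donors".
- **Management and Monitoring.** "The mother will be evaluated by the vital signs and other signs of headache, palpitation, dizziness, GI upset", in a list that is left open at its end. For the fetus, "The fetus will be monitored by the cardiotocography". Liquor is inspected at amniotomy, and "Persistent abnormal fetal CTG or deeply stained liquor will be referred to theater for cesarean section".
- **Both groups will be compared regarding.** The maternal safety item reads "Incidence of maternal complications, namely; headache, nausea, postpartum hemorrhage". The neonatal item reads "Neonatal outcome through Apgar score at 1 and 5 minutes after delivery". Cesarean section, yes or no, is also compared.

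Two further facts matter. The Introduction describes NO as relaxing vascular smooth muscle and causing vasodilation. The Method section gives dinoprostone to both groups, so the patch is the only planned difference between them.

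**The concern.** The objective is open-ended and the conclusion it promises is strong, but the maternal comparison is short and, through the word *namely*, reads as complete. The items it leaves out include those that the protocol's own account of the drug would point to first. A vasodilator could be expected to show itself in blood pressure and pulse, dizziness and palpitation. Staff are asked to look for these, but no between-group comparison of them is planned.

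The quality of the tolerability statement is at stake. If the published comparison covers only the three named maternal events, it says little about the systemic effect of the patch. If other events are added once the data are in, the choice of which to show is open to selection. This is not a detail left blank for a SAP. The protocol states a list, and a SAP that followed it would inherit the gap.

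**Working it through.** The plan gives no figure for safety events, so there is none to reproduce. The check sets the monitoring section beside the comparison list.

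| Item | Monitored | Compared between groups |
|---|---|---|
| Headache | yes | yes |
| GI upset | yes | in part, as nausea |
| Palpitation | yes | no |
| Dizziness | yes | no |
| Maternal vital signs | yes | no |
| CTG | yes | only through cesarean section, if persistently abnormal |
| Meconium-stained liquor | yes, at amniotomy | only through cesarean section, if deeply stained |
| Postpartum hemorrhage | not named there | yes |
| Apgar at 1 and 5 minutes | not named there | yes |

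**Count.** Four maternal symptoms are named for monitoring: one is compared in full, one in part, two not at all. Vital signs are a further omission.

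**Why the comparison by arm matters.** Dinoprostone is given in both arms, so an event rate alone does not show what the patch did. As an illustration with assumed rates, take 50 women per arm (100 at 1:1). Rates of 5% and 15% give 2.5 + 7.5 = 10 expected events in 100 women. Rates of 10% and 10% give 5 + 5 = 10. The overall figure is 10% in both cases, but the difference between arms is 10 points in one and 0 in the other.

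**What 50 per arm could show.** The event rates here are assumptions; the protocol gives none. Half-width of the 95% CI = 1.96 × √[p1(1−p1)/50 + p2(1−p2)/50]. Power is for the two-sided 5% test of two proportions.

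| Assumed rates | Difference | 95% CI half-width | Power |
|---|---|---|---|
| 5% v 15% | 10 points | 1.96 × √0.00350 = 11.6 points | 38% |
| 5% v 20% | 15 points | 1.96 × √0.00415 = 12.6 points | 62% |
| 5% v 25% | 20 points | 1.96 × √0.00470 = 13.4 points | 81% |

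If an arm of 50 has no events of a given kind, the one-sided 95% upper limit for its rate is 1 − 0.05^(1/50) = 5.8%.

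The trial could therefore reveal a large excess of a symptom such as dizziness, but could not exclude a moderate one. That favors presenting intervals over relying on tests.

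**The case against.** The case on the other side has real force in several places.

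- **The three maternal events are not the whole safety comparison.** A reader might infer that they are. The word *namely* governs only the maternal item, and Apgar scores and cesarean section are compared as well. This stands.
- **Unlisted events need not go unreported.** A reader might infer that palpitation or dizziness would never appear in the results. The objective commits to observing and reporting side effects, so a descriptive account fits the text. This stands. What is missing is a planned comparison, and the objective does not say that its report will be by arm.
- **Fetal compromise is not ignored.** Persistent CTG abnormality and deep staining lead to cesarean section, which is compared. This stands in part. Cesarean section has many causes, so it cannot show whether CTG abnormality differed by arm, and transient abnormality or lighter staining does not pass through it.
- **The list may be unfinished.** The maternal item ends on a comma, so *namely* may be loose drafting. That is possible, but the printed list is the only one an analyst has, and an unfinished list also needs completing.
- **Monitoring is bedside care, and not every monitored variable must be an outcome.** True in general. Here, though, the omitted items are the ones most closely tied to the drug's stated action, and the protocol claims it will establish tolerability.

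**Conclusion.** The point holds in a limited form. Palpitation, dizziness and maternal vital signs are monitored but not planned for between-group comparison. CTG findings and liquor enter only indirectly, through cesarean section. The list therefore falls short of the stated safety and tolerability objective, and the three sections should be aligned.

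The size is moderate: two of four named symptoms and the vital signs are absent, and one symptom is partly covered. The primary comparison, the error rate and the sample size are not touched. The conclusion rests on reading the maternal list as complete, as its wording suggests, and on the Introduction's description of NO as a vasodilator. The documents do not support the stronger claims that these harms will go unreported or that fetal safety is not compared.

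**What to change.** Extend the list of comparisons to match what is already monitored. Add palpitation, dizziness, nausea or other GI upset (replacing nausea alone), maternal vital signs, abnormal CTG and meconium-stained liquor. Keep headache, postpartum hemorrhage, Apgar at 1 and 5 minutes and cesarean section.

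- **Binary events:** number and percentage by arm, with the difference and its 95% CI.
- **Vital signs:** change from admission, with a mean or median difference between arms. A risk difference does not suit them. The Assessment section already takes vital signs at the outset, which supplies a baseline.
- **Apgar:** leave as a score, as now listed.

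**Cost.** Routine monitoring is not yet trial data. Each item needs a simple definition, a recording time and a place on the case form. Liquor also needs a stated denominator, because the protocol mentions it only for women who undergo amniotomy.

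The longer list also means more comparisons. Apart from cesarean section there would be seven binary events (headache, palpitation, dizziness, GI upset, postpartum hemorrhage, abnormal CTG, stained liquor). If each were tested at 5% and they were independent, the chance of at least one false positive would be 1 − 0.95^7 = 30%, against 1 − 0.95^3 = 14% for the three now named. Presenting these as estimates with intervals, and saying in advance that they are descriptive of harm and not confirmatory, deals with that. The intervals will be wide at about 50 women per arm, and the claim to establish safety should be worded to match.
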